#### J07BB Influenza vaccines

ATC code	Name
J07BB01	influenza, inactivated, whole virus
J07BB02	influenza, inactivated, split virus or surface antigen
J07BB03	influenza, live attenuated

**Figure 14: Most detailed ATC codes for vaccines**

For future benefit risk analyses we may need additional information on the vaccines (e.g. valence, excipients). This information needs to be retrieved from other sources, therefore we will need a vaccine ontology that can provide additional information on the vaccines which may be useful for analysis as well as to enable the fingerprinting across multiple databases.

## Analysis of vaccination fingerprint

The vaccine fingerprint will be described by using vaccination coverage estimates as well as the number of doses per person. To fingerprint the datasources in terms of vaccine coverage /uptake data we will:

Estimate coverage by age, gender, calendar year of the following vaccinations and compare these to the monitoring data from WHO, the ECDC funded VENICE II consortium^5 and available national statistics: Bacille Calmette-Guérin (BCG) vaccine, the third dose of diphtheria and tetanus toxoid and pertussis vaccine (DTP3), the third dose of polio vaccine — either oral polio vaccine or inactivated polio vaccine, the first dose diphtheria and tetanus toxoid and pertussis vaccine (DTP1) and the third dose of haemophilus influenza type b (Hib3), seasonal Influenza (compared to VENICE) and the first dose and third dose of human papillomavirus vaccinations (HPV). These vaccines are also reported to WHO and provide for benchmark

---

 [http://www.whocc.no/atc\\_ddd\\_index/](http://www.whocc.no/atc_ddd_index/)

 <http://www.who.int/immunization/en/>

 [http://venice.cineca.org/the\\_project.html](http://venice.cineca.org/the_project.html)

 [VENICE II: Go on combining our efforts towards a European common vaccination policy! F D'Ancona on behalf of VENICE II group. Eurosurveillance, 2009, vol. 14 n.12: Seasonal influenza immunisation in Europe. Overview of recommendations and vaccination coverage for three seasons: pre-pandemic \(2008/09\), pandemic \(2009/10\) and post-pandemic \(2010/11\). J Mereckiene, S Cotter, A Nicoll, P Lopalco, T Noori, J T Weber, F D'Ancona, D Lévy-Bruhl, L Dematte, C Giambi, P Valentiner-Branth, I Stankiewicz, E Appelgren, D O'Flanagan, the VENICE project gatekeepers group. Eurosurveillance, 19 \(16\) 2014.](#)

 [Health technology assessments on human papillomavirus vaccinations in Europe: a survey from Venice network. Frédérique Dorléans, Daniel Lévy-Bruhl, Cristina Giambi, Fortunato D'Ancona, Giuseppe La Torre, Suzanne Cotter, Jolita Mereckiene, Pawel Stefanoff, Eva Appelgren and the Vaccine European New Integrated Collaboration Effort \(VENICE II\) project gatekeepers. Italian Journal of Public Health, Volume 9, N. 1 \(2012\)](#)

---

Assess timing of childhood immunizations in databases (by age) and compare these with local recommended schedule.

For vaccination fingerprint we will look at describing coverage at 12, 24, 48 and 120 months (BCG, DTP, polio, Hib), and a cumulative approach (Kaplan Meier) for birth cohorts. For HPV, we will assess coverage at age 16. For seasonal influenza vaccination, we will assess coverage by year of age. Timing of vaccinations will be described by plots for age of vaccination by type and dose of vaccine and this will be compared with the information in the vaccine schedules.

---

## APPENDIX 2: POC EVALUATION (SYSTEM TESTING FRAMEWORK)

### Methods for the evaluation of the system: POC Evaluation Framework

**The POC evaluation will be conducted by the POC evaluation team which is independent from the study teams. The team is coordinated by prof. [name] (SURREY) and dr. [name] (P-95)**

**Purpose of the POC evaluation:** POC evaluation focuses on combining, analysing and reporting on the performance and knowledge generated during the performance of the POC experiments, to inform the reliability and sustainability of a post-ADVANCE platform, as defined in the Vision and Mission. Conceptually, POC evaluation aims to evaluate the “whole system”, including the technology, the framework, and the process used in the POC to perform vaccine B/R assessment.

The POC evaluation is therefore based on a systematic assessment whether the concept designed and tested through conducting the POC is *acceptable and good enough to be recommended for “release into production”* in the ultimate ADVANCE blueprint. Thus, the focus will be on whether ADVANCE adds value in terms of: (1) *Speed to obtain results*; (2) *Fostering productive collaboration*; (3) *Enabling good science*.

#### OBJECTIVES:

- 1. Feasibility and effectiveness:** Demonstrate that the selected POC cases can be implemented (more) effectively using the ADVANCE Framework  
“assess the level of attainment of the ADVANCE mission (and vision) statements, through collecting, analysing and reporting on the outputs of the POCs”  
Questions to be answered by the evaluation:  
I: Is it doable?  
*Are the basic conditions and processes sufficient/enabling for ADVANCE to operate?*  
II: Is the output meaningful?  
*Is the evidence produced meaningful for the purpose of B/R decision making?*  
III: Adds-value, cost-effective?  
*Is the value/cost ratio in maintaining and performing a study improved (i.e. greater cost effectiveness), as perceived by the partners in the collaboration?*
- 2. Scaling:** Derive general guidelines to guide the implementation of the evidence creation process for any Research Question (RQ) in the future (i.e.: developing the Blueprint: how to design and conduct any vaccine B/R study based on the ADVANCE Framework)  
Questions to be answered by the evaluation:  
IV: Is it generalizable and scalable?  
*Can ADVANCE be used and perform equally when addressing other B/R questions in other vaccines, and disease areas?*

In a nutshell, the ADVANCE Evaluation Framework offers quality indicators, methods, and a timeplan. It spans five evaluation areas, which follow loosely the POC work progression\* (i.e. concurrent with the POC timeplan), a number of dimensions with the corresponding sets of indicators and related datasets, and the methods with which these will be measured\*\*:

---

## AREA 1: ADVANCE Process performance and IT infrastructure

[figure not shown]
The *Process & IT evaluation* covers both **Technical infrastructure** and **Process Workflows** at the same time, and follows the *4 stages* of the overall process: protocol writing, data extraction, transformation, analysis.

**Evaluating the Research protocol formation process.** The ultimate goal of a process evaluation is to illuminate the pathways linking what starts as a Research Question (theoretical/scientific protocol), and its underlying causal assumptions, to the outcomes produced. In order to achieve this, it is necessary to understand:

- The implementation, both in terms of how the RQ was implemented (new or “tech-enhanced/ IT-enabled” protocol) and the quality of what was delivered;
- the mechanisms of impact linking RQ implementation activities to outcomes;
- how the context in which the RQ is investigated (e.g. external factors) affects both what is implemented and how outcomes are achieved.

For this, the **ISO/IEC 15504 (SPICE)** standard can be followed, which is a framework for the process assessment that defines a **process dimension** and a **capability dimension**.

**Evaluating the IT infrastructure.** The evaluation measures are built on provisions included in the ISO/IEC 25010 System and Software Product Quality standard (part of ISO/IEC 25000 - SQuaRE). This standard defines internal metrics (static, do not rely on software execution) and external metrics (applicable to running software). It comprises 8 quality characteristics:

IT infrastructure metrics: a. User satisfaction; b. Processing capacity and speed; c. Flexibility; d. Resources and effort; e. CPU times for analyses, loading; f. Failure rates, errors, black outs, off line time; g. Gaps in IT tools and functionality (e.g. document review platform, archiving and version control)

A1 Evaluation dimensions: Time, Cost, Data Access, IT infrastructure, Data sharing, Privacy and ethics, Data processing, Data protection, Data privacy, Qualified study personnel, Accessibility of data (study results and resources)

## AREA 2: Scientific validity and innovation

This area covers **Data sources**; **Methods**; and **Innovation potential**.

Approach: Consultation with Experts, Scientific advisory committee

---

Flexibility/adaptability: how flexible to address the new guidance and requirements WP3 use cases, flu guidance, new vaccines.

Scientific validity: SAB review and feed-back

- Quality of research questions
- Early scientific input in the formulation of relevant B/R framework prior to the protocol development

Innovation aspects:

What has been done that was not already done before?

What has been developed that would not be possible to do without ADVANCE?

What was developed in the POC that can become a tool or asset in the real world?

What was not tested in the POC, but should have been?

Is there potential to implement or support continuous B/R monitoring

A2 Evaluation dimensions: Science / Scientific quality, Data access, Flexibility / generalizability, Scientific validity, Documentation, Reproducibility, Innovation (multiple aspects)

### **AREA 3: Quality standards, regulatory compliance and legal robustness**

**Compliance**: with legislation, standards, approvals to run the study

**Quality of** process, data management, data integrity, privacy and security, validation of the writing, validation of the programming, number of amendments to the protocols, number of errors

A3 Evaluation dimensions: Compliance, Ethics, Quality, Quality control, Confidentiality, Data protection, Privacy

### **AREA 4: Stakeholder satisfaction**

Does the POC answer the needs of the different stakeholders and perspectives in terms of decision B/R focus, and the satisfaction and added value of working collaboratively?

**Acceptability** of study team, study proposal, workflow and report by stakeholders (stakeholder feedback survey), including decision process.

Before and after survey: Needs satisfied

**Transparency** as perceived by all stakeholders: What information can be made public (protocol, authors), how much time after it was done, is the information understandable, the decision-making processes (minutes, agendas), whose interests are involved / who benefits.

A4 Evaluation dimensions: Acceptability, Transparency, Satisfaction, Public trust

### **AREA 5: Code of conduct and Collaboration**

This area covers the **Code of conduct**, **Collaboration** and **Rules of governance**.

An important aspect of the evaluation will be the **European network** (regulators and standards organisations, as well as industry) and the enablement/facilitation or strengthening of cross-discipline/cross-sector international collaboration – including sustainable collaboration, and collaboration opportunities.

---

Before and after survey: Perceived added value of collaboration

A5 Evaluation dimensions: Satisfaction, Interoperability, Network building, Trust

**Methods of data collection** for the evaluation activities include:

- Surveys, collecting mass feedback from users and stakeholders
- Review and analysis of meeting minutes
- Interviews with experts and stakeholders
- Quantitative data analysis of existing data sets

A detailed description of the specific methods to be used for each dimension/indicator is provided in the *ADVANCE Evaluation Indicators* table\*\*.

*\*The evaluation process should be as observational as possible (non-interventional) and PIs and study teams should operate as per process rather than towards fulfilling the indicators requirements.*

*\*\*A detailed description of all the **indicators, together with specific methods and requirements**, is provided in a separate spreadsheet document (*ADVANCE Evaluation Indicators*)*

---

## APPENDIX 3: CLINICAL DEFINITIONS

### SOMNOLENCE

Drowsiness

Reduced interest in surroundings or increased sleeping:

Grade 1: Sleepier than usual or less interested in surroundings

Grade 2: Not interested in surroundings or did not wake up for a feed/meal

Grade 3: Sleeping most of the time or difficult to wake up

---

## APPENDIX 4: PERTUSSIS VACCINES

ATC code	ATC name	Whole cell or a-cell
J07AJ52	Pertussis, purified antigen, combinations with toxoids	aP
J07CA02	Diphtheria-pertussis-poliomyelitis-tetanus	aP
J07CA06	Diphtheria-hemophilus influenzae B-pertussis-poliomyelitis-tetanus	aP
J07CA09	Diphtheria-hemophilus influenzae B-pertussis-poliomyelitis-tetanus-hepatitis B	aP
J07AG52	Hemophilus influenzae B, combinations with pertussis and toxoids	aP
J07CA05	Diphtheria-hepatitis B-pertussis-tetanus	wP
J07AJ01	Pertussis	wP
J07AJ02	Pertussis	aP
J07AJ51	Pertussis	wP
J07CA11	Diphtheria-Hemophilus influenzae B-pertussis-tetanus-hepatitis B	?
J07CA12	Diphtheria-pertussis-poliomyelitis-tetanus-hepatitis B	?
J07CA13	Diphtheria-hemophilus influenzae B-pertussis-tetanus-hepatitis B-meningococcus A + C	?
J07AG	Hemophilus influenzae B, combinations with pertussis and toxoids	wP

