### **PERTUSSIS VACCINATION SCHEDULES IN EUROPE**

Between 2004 and 2015 several countries switched from wP to aP vaccines for infants and children. All other countries in Europe switched to aP vaccines prior to 2006 (starting in the 1990s for some countries). As of March 2015, all countries except Poland use exclusively aP vaccines. In most cases, the switch to aP vaccines was conducted over a narrow age-cohort, while only in very few cases, such as Poland, the switch occurred, or is occurring progressively over years. Different types of vaccines are being used. As part of the coverage pillar the way participating countries switched should be described.

Since the start of the introduction of pertussis vaccine in the 1940s, many countries have tended to adapt and customize the schedules of their vaccination programs, adding and removing doses, changing ages of primary and booster schedules, with or without catch-up campaigns, and transitioning from wP to aP vaccines for all doses, for one or more booster doses only, or not yet at all. As a result, pertussis vaccine schedules vary largely across Europe.

For detailed information on the schedules currently used in Europe, see Figure 2 and for more details see European Centre for Disease Prevention and Control (ECDC)-website (<http://vaccine-schedule.ecdc.europa.eu/Pages/Scheduler.aspx>).

---

 [http://www.nap.edu/openbook.php?record\\_id=13164&page=529](http://www.nap.edu/openbook.php?record_id=13164&page=529)

Schedule type	First year of life			Second year of life	Third year of life	Preschool booster	Adolescent booster	Country
	From 6 weeks to 6 months		Around first birthday					
'2p+1'	P1	P2	B1			B2	B3	F, IT, FI, NO, IS, SK
								SE, DK, RO, AT
'3p+1'	P1	P2	P3	B1		B2	B3	BE, BG, CZ, EE, DE, GR, HU, LI, LU,
				B1		B2		HR, CY, LV, LI, MT, NL, PL, PT, SI, ES
					B1			UK
						B1	B2	IE
Vaccine combination generally used in EU/EEA	
 
DTaP-IPV-HepB/Hib ('hexavalent')
 
DTaP-IPV/Hib ('pentavalent')
 
DTaP-IPV ('tetraivalent')
 
DTwP-IPV/Hib ('whole-cell pertussis combo')
 
Hep B (used in conjunction with pentavalent)
 
			
 
Hib-MenC combo
 
	
 
DTaP-IPV
 
Tdap
 
Tdap-IPV
 
Tdap
 
	
 
Td
 
Tdap
 
Tdap-IPV
 
		

P=primary dose; B=booster dose

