#### OPERATIONALIZATION

Vaccinations will be obtained from the databases by using names of vaccines and database specific codes. Vaccines will be categorized as wP, aP or unknown. There will be no further stratification in brand or product name (see Appendix 4 for categorization).

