  - The current methodology will not account for differences in vaccination schedules: different countries use different vaccines and schedules that may have changed over time. ATC codes will be used to identify which types of vaccines were used; this will allow stratification on vaccine types. Further, risks on schedule level will not be evaluated but will be evaluated on a dose level as each case is followed after each dose given.
  - Misclassification or missing information on vaccinations and events is a common limitation of observational studies conducted in electronic healthcare databases. Missingness and misclassification will be carefully followed and attempts will be made to implement data cleaning procedures (e.g. probability of wP or aP vaccine given the time of administration, dose according to timing in vaccination schedule, etc). Records with missing dates (i.e. birthdates, data of vaccination, date of event occurring) will be excluded. ATC code is a mandatory data field. A missing dose information will be derived (i.e., dose will be per recommendation, as determined by the database custodian based on knowledge of the local immunization schedule and as documented in an analytic variable generated for the purpose of the study).
  - aP and wP vaccine administration could have been overlapping. The period of potential overlap in a database will be excluded if aP or wP vaccine type information is missing (i.e. database entry is only referring to 'pertussis vaccine' and aP or wP is not specified).
  - The smallest possible time unit in electronic healthcare databases is 'days'. This could potentially make it difficult to judge whether vaccination happened before the event or vice versa when recorded on the same day. In this study, it is assumed a priori that vaccination occurs before the event whenever they are recorded on the same day, so the vaccination day is classified as risk period and starting at Day 0.

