## Vaccine fingerprinting

---

Initial discussions with the databases showed that most databases will have information on the vaccinetype and the ATC code or at least part of it. In the Anatomical Therapeutic Chemical (ATC) classification system, the active substances are divided into different groups according to the organ or system on which they act and their therapeutic, pharmacological and chemical properties. Vaccines are coded in different Anatomical groups although the majority are part of the therapeutic subgroup J07.

The divisions are made between bacterial (J07A), viral (J07B), bacterial & viral (J07C), other vaccines (J07D) and cancer vaccines (in L03). Bacterial vaccines are divided in 14 subgroups, viral vaccines are divided in 13 subgroups, grouping is based on the vaccine preventable disease. Within the groupings the most detailed level finishes with the type of antigen.

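### Appendix 4 fixes ATC code J07CA06 as acellular although the protocol lists a whole-cell vaccine of the same composition, and it gives J07AG52 and J07AG one name with opposite labels

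*Protocol*

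**What the plan says.** - **Classification rule.** Protocol section 7.2.7.1 (Operationalization) sorts vaccines into wP, aP or unknown and points to the appendix: "There will be no further stratification in brand or product name (see Appendix 4 for categorization". On the source of the records it says: "Vaccinations will be obtained from the databases by using names of vaccines and database specific codes".
- **Deciding field.** Section 7.2.9 states "ATC codes will be used to identify which types of vaccines were used" and "ATC code is a mandatory data field".
- **The table.** Appendix 4 labels J07CA06, "Diphtheria-hemophilus influenzae B-pertussis-poliomyelitis-tetanus", as aP, with no condition on date, country or product. Haemophilus influenzae B combined with pertussis and toxoids appears twice under one name: J07AG52 is aP and J07AG is wP. Three other combinations (J07CA11, J07CA12, J07CA13) carry a question mark.
- **Vaccines of that composition.** The schedule table in section 5 (Figure 2) lists, among combinations generally used in the EU/EEA, both "DTaP-IPV/Hib ('pentavalent" and "DTwP-IPV/Hib ('whole-cell pertussis combo".
- **Completeness of codes.** Appendix 1 (Vaccine fingerprinting) expects that "most databases will have information on the vaccinetype and the ATC code or at least part of it".

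**The concern.** Vaccine type is the exposure of the whole study. J07CA06 names antigens only, and the protocol's own vaccine list shows that those antigens occur with either pertussis component. The authors had a way to mark undetermined codes, the question mark, but did not use it here.

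A whole-cell dose recorded under J07CA06 would bring its person-time and its reactions into the aP group. Section 5 reports wP as the more reactogenic vaccine, so aP rates would rise and the wP/aP contrast passed to the benefit-risk model would shrink. The same dose would be lost to the wP SCCS estimate, which sections 7.2.1 and 7.2.8.3 carry to databases without wP data. In the extreme, a database that does hold wP doses would appear to hold none.

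**Working it through.** The protocol states no figure for misclassification, so there is none to reproduce. The check has three parts.

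**1. Does the code determine the type?** J07CA06 covers diphtheria, Hib, pertussis, polio and tetanus. The section 5 list contains this set once as acellular and once as whole-cell. It does not determine the type. For J07AG52 and J07AG the names are identical and the labels opposite, so at least one label cannot rest on the name.

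**2. Do other provisions correct a wrong label?**
- Section 7.2.5 removes person-time during the switch period. Earlier wP-only years stay in a study period that starts in 1990. Section 5 says several countries switched between 2004 and 2015.
- Section 7.2.9 excludes overlap time only where the aP/wP type is missing. A J07CA06 record has a definite label, so its type is not missing.
- Section 7.2.9 also undertakes to try data cleaning, for example by the likelihood of wP or aP at the date of administration. No rule says that this, or a recorded product name, prevails over Appendix 4.

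**3. How large could the effect be?** Inputs from section 5 (Safety Studies):
- HHE after dose 1: wP 0.12%, aP 0.03% (Dutch questionnaire study)
- Febrile convulsions after dose 4: wP 0.06%, aP 0.02% (same study)
- Fever of at least 37.8 °C: wP 27.3%, aP 4.2% after the first dose (US study of 13 aP vaccines)

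Let f be the share of aP-labelled doses that are truly wP. The documents do not give f; 5% to 30% is assumed. The mislabelled doses are taken to carry the same wP risk as those correctly labelled.

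Observed aP risk = (1 − f) × aP + f × wP. Observed ratio = wP / observed aP risk.

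HHE at f = 0.05: 0.95 × 0.03 + 0.05 × 0.12 = 0.0345%, ratio 0.12 / 0.0345 = 3.48. At f = 0.30: 0.70 × 0.03 + 0.30 × 0.12 = 0.057%, ratio 0.12 / 0.057 = 2.11.

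| wP/aP ratio | f = 0 | 5% | 10% | 20% | 30% |
|---|---|---|---|---|---|
| HHE, dose 1 | 4.00 | 3.48 | 3.08 | 2.50 | 2.11 |
| Febrile convulsions, dose 4 | 3.00 | 2.73 | 2.50 | 2.14 | 1.88 |
| Fever, dose 1 | 6.50 | 5.10 | 4.19 | 3.10 | 2.45 |

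At f = 10% the observed aP risks rise 1.30-fold (0.039%), 1.20-fold (0.024%) and 1.55-fold (6.51%) respectively.

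**The case against.** The strongest reply has four parts.

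- **Names may already settle the type.** Section 7.2.7.1 obtains vaccinations by name and local code. Its remark on brand limits analysis strata and does not say that names are ignored. Table 5 treats DTaP and DTwP as separate vaccine types and assesses granularity by vaccine type, ATC code and brand. This stands in part: the information may be there, but its precedence over the ATC label is not stated.
- **Checks exist.** The cleaning step in section 7.2.9 addresses misclassification as well as missing data, and custodians report when both vaccines were in use. A reader might infer that nothing would catch the error. The documents do not support that. They do leave the check as an attempt without a rule.
- **Use in the study databases is not shown.** The Figure 2 list is an EU/EEA overview from October 2015, and section 5 says that only Poland was then not exclusively on aP. The protocol gives neither the composition nor the ATC coding of the wP vaccines used in the eligible countries. This stands: the misclassification is conditional on such doses being recorded under J07CA06.
- **Rates are stratified.** Section 7.2.8.3 splits rates by database and calendar year, so mislabelled doses would cluster in pre-switch years and could be noticed. This stands for the fine strata. Section 7.2.8.1 provides for aggregation when numerators are zero, which is likeliest for rare events such as HHE.

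The protocol also says in section 7.2.9 that its results may not be the true estimates. That lowers the clinical stakes but does not remove a contradiction in the exposure definition.

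**Conclusion.** The contradiction is established for J07CA06 and for the pair J07AG52/J07AG. Because the appendix is the stated classifier and no rule overrides it, a whole-cell dose under J07CA06 would be analysed as aP, biasing the wP/aP contrast towards 1. The effect on the wP SCCS ratio is loss of doses; the documents do not show that the remaining estimate is biased. The size is unknown. The HHE ratio of 3.5 to 2.1 in place of 4.0 rests on the assumed 5% to 30% share and on the section 5 risks.

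Three stronger readings are tempting but unsupported:
- **That all polio-containing codes labelled aP are wrong.** For J07CA02 and J07CA09 the section 5 list shows only acellular versions, and it shows no acellular product matching J07CA05, which is labelled wP. Caution is reasonable there, but error is not shown.
- **That shortened J07AG52 codes will flip to wP.** Appendix 1 says some databases may hold part of the code, not that it is cut to five characters. That route would also run in the opposite direction, from aP to wP.
- **That Dutch rates would more than double.** Pooling 9 wP years and 10 aP years (NL_IPCI, 1996 to 2014) with every wP dose miscoded gives HHE of (9 × 0.12 + 10 × 0.03) / 19 = 0.073% against 0.03%. This assumes complete miscoding, equal doses per year and pooling over years that the plan stratifies.

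**What to change.** 1. In Appendix 4, mark J07CA06 and the bare group code J07AG as *type not determined by ATC*. As a precaution, treat other codes whose name does not fix the type, including the question-mark rows, in the same way.
2. For these codes, assign type from the recorded vaccine type, product name or local code. Failing that, use the database's dated switch from wP to aP, building on the dates custodians are asked to supply under section 7.2.5. Failing that, use unknown.
3. State in section 7.2.7.1 that this rule takes precedence over the ATC label.
4. Before events are linked, tabulate assigned type by calendar year and database against the switch date.

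The cost is one revised table, one mapping step in the common script and one descriptive table per database. Some doses will move to unknown, with a loss of precision.
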